8.5.1.1. Criteria for the Calculation of Apparent Terminal Elimination Rate Constant and Half-life

The start of the terminal elimination phase for each subject will be defined by visual inspection and generally will be the first point at which there is no systematic deviation from the log-linear decline in concentrations.

The apparent terminal elimination rate constant (λ_z) will only be calculated when a reliable estimate can be obtained using at least 3 data points, preferably not including C_{max}, and the adjusted coefficient for determination of exponential fit (R²-adj) of the regression line is ≥ 0.8 .

Parameters requiring λ_z for their calculation (eg, $AUC_{0-\infty}$, $t_{1/2}$, CL/F , V_z/F) will only be calculated if the R^2 -adj value of the regression line is ≥ 0.8 .

The following regression-related diagnostic PK parameters will be determined, when possible:

Parameter	Units	Definition
$\%AUC_{\text{extrap}}$	%	percentage of AUC due to extrapolation from the last quantifiable concentration to infinity
λ_z	1/h	apparent terminal elimination rate constant
λ_z Upper	h	end of exponential fit
λ_z Lower	h	start of exponential fit
λ_z N	NA	number of data points included in the log-linear regression
λ_z Span Ratio	NA	time period over which λ_z was determined as a ratio of $t_{1/2}$
R^2 -adj	NA	adjusted coefficient for determination of exponential fit

Where possible, the span of time used in the determination of λ_z (ie, the difference between λ_z Upper and λ_z Lower) should be ≥ 2 half-lives. If the λ_z Span Ratio is <2 , the robustness of the $t_{1/2}$ values will be discussed in the clinical study report (CSR).

8.5.1.2. Criteria for Calculation and Reporting of Area Under the Concentration-time Curve

The minimum requirement for the calculation of area under the concentration-time curve (AUC) will be the inclusion of at least 3 consecutive concentrations above the lower limit of quantification. If there are only 3 consecutive concentrations, at least 1 should follow C_{max} . An exception may be made for metabolites, where C_{max} may be the last timepoint.

If the extrapolated area is $>20\%$, AUC_{inf} (and derived parameters) will be listed but flagged and excluded from statistics.

If AUC_{inf} cannot be determined reliably for all subjects, an alternative AUC measure, such as AUC to a fixed timepoint or $AUC_{0-\text{tlast}}$, may be used in the statistical analysis.

8.5.1.3. Criteria for Handling Concentration Below the Limit of Quantification or Missing Concentrations for Pharmacokinetic Analysis

Plasma concentrations below the limit of quantification (BLQ) will be assigned a value of 0 before the first measurable concentration and thereafter BLQ concentrations will be treated as missing. The following rules apply to the specific situations defined below:

- If an entire concentration-time profile is BLQ, it will be excluded from PK analysis.
- Where 2 or more consecutive concentrations are BLQ at the end of a profile, the profile will be deemed to have terminated and any further quantifiable concentrations will be

set to missing for the calculation of the PK parameters, unless they are considered to be a true characteristic of the profile of the drug.

- If a predose plasma concentration is missing, it will be set to 0 by default within Phoenix WinNonlin.

8.5.1.4. Treatment of Outliers in Pharmacokinetic Analysis

If a value is considered to be anomalous due to being inconsistent with the expected PK profile, it may be appropriate to exclude the value from the PK analysis. However, the exclusion of any data must have strong justification and will be documented in the CSR.

Any quantifiable predose concentration value in the first treatment period will be considered anomalous and set to missing for the PK analysis. This will be set to 0 by default in Phoenix WinNonlin.

If the predose concentration is $>5\%$ of C_{max} in the second treatment period, all PK concentration and parameter data will be excluded from the summary statistics and statistical analysis for that period.

8.5.2. Presentation of Pharmacokinetic Data

All PK concentrations and parameters will be listed.

Summary tables, arithmetic mean (+ standard deviation [SD]) figures, overlaying individual figures, and individual figures by treatment and time postdose will be provided for plasma PK concentrations. All figures will be produced on both linear-linear and linear-logarithmic scales, with the exception of figures across all days, which will be produced on the linear-linear scale only. The $\pm SD$ bars will only be displayed on the linear-linear scale.

Summary tables by treatment will be provided for all PK parameters, with the exception of diagnostic regression-related PK parameters. Separate summary tables by treatment and time interval will be provided for excretion parameters and cumulative excretion parameters.

A subject may be excluded from the PK summary statistics and statistical analysis if the subject has an AE of vomiting that occurs at or before 2 times the median t_{max} .

If the actual time of sample collection deviates from the nominal time by more than $\pm 10\%$, the concentration will be flagged, but included in the summary statistics.

Individual concentrations deemed to be anomalous will be flagged in the listings and excluded from the summary statistics.

For plasma concentration data the following rules will apply:

- Values that are BLQ will be set to 0 for the calculation of summary statistics.
- Arithmetic mean or median values that are BLQ will be presented as 0.

For PK parameters the following rule will apply:

- Geometric mean and coefficient of variation will not be calculated for t_{last} , t_{max} .

8.5.3. Pharmacokinetic Statistical Methodology

A statistical analysis will be conducted to investigate the drug-drug interaction, the primary PK parameters will be AUC_{inf} , $AUC_{0-t_{last}}$, and C_{max} for sotorasib on each of the dosing days. All other PK parameters will be regarded as secondary and will not be subject to inferential statistical analysis.

A linear mixed effects model will be used to analyze log-transformed primary PK parameters. The model will assume fixed effect for treatment and a random effect for subject. Geometric mean ratios for C_{max} and AUC values and associated 90% confidence intervals (Test/Reference) will be estimated. The “Reference” treatment for PK analysis will be sotorasib administered alone with water, while the “Test” treatment will be omeprazole administered in combination with sotorasib and an acidic beverage.

For each PK parameter separately, the least squares mean (LSM) for each treatment, difference in LSMS between the test and reference treatments, and corresponding 90% confidence interval (CI) will be calculated; these values will then be back-transformed to give the geometric least squares mean (GLSM), ratio of GLSMs, and corresponding 90% CI.

Additionally, the pooled estimate (across all treatments) of the within-subject CV will be calculated, and residual plots will be produced to assess the adequacy of the model(s) fitted.

Examples of the SAS code that will be used are as follows:

Mixed Model Analysis

```
proc mixed data = <data in>;
  by parcatln parcat1 pkday paramn param;
  class trtan usubjid;
  model l_pk = trtan aperiod trtseqp / cl residual ddfm = kr;
  lsmeans trtan / cl pdiff = control('1') alpha = 0.1;
  random intercept / subject = usubjid(trtseqp);
  ods output lsmeans = <data out>;
  ods output diffs = <data out>;
  ods output covparms = <data out>;
run;
```

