8.3. Pharmacokinetic Analyses

The plasma PK parameters of sotorasib on Days 1 and 9 will be calculated using standard noncompartmental methods.

The primary PK parameters are C_{max} , AUC_{inf} , and AUC_{last} for sotorasib. A linear mixed-effects model will be used to analyze log-transformed primary PK parameters. The model will assume fixed effect for treatment and a random effect for subject. Geometric mean ratios for C_{max} and AUC values and associated 90% confidence intervals (Test/Reference) will be estimated. The "Reference" treatment for PK analysis will be sotorasib administered alone with water, while the "Test" treatment will be omeprazole administered in combination with sotorasib and an acidic beverage.

Additional parameters may be calculated. Specific details will be presented in the Statistical Analysis Plan for this study.

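### The example SAS code in SAP 8.5.3 does not match the stated primary PK model and does not suit a study with one fixed sequence

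*SAP*

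**What the plan says.** Protocol 8.3 gives the model for log-transformed Cmax, AUCinf and AUClast: "The model will assume fixed effect for treatment and a random effect for subject". SAP 8.5.3 repeats that sentence and asks for LS means, their difference and a 90% CI, all back-transformed. It also says: "Additionally, the pooled estimate (across all treatments) of the within-subject CV will be calculated".

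The code follows under the line "Examples of the SAS code that will be used are as follows". Four statements matter here:

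- BY: "by parcatln parcat1 pkday paramn param"
- CLASS: "class trtan usubjid"
- MODEL: "model l_pk = trtan aperiod trtseqp / cl residual ddfm = kr"
- RANDOM: "random intercept / subject = usubjid(trtseqp", which nests subject in sequence.

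The design has one sequence. Protocol 5.5 calls it nonrandomized with a fixed treatment order, and SAP 4 has all subjects take sotorasib alone on Day 1 and the combination on Day 9. SAP 10 declares no significant changes from the protocol's analyses.

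**The concern.** The words and the code describe different models. The code has the form used for a crossover with several sequences, where treatment can be separated from period because different subjects take the treatments in different orders. Here nobody does, so a period term competes with treatment for the same information and a sequence term carries none. The BY statement raises a separate question: if it splits the data by dosing day, the two treatments never meet in one fit.

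This is the only code given for the only inferential analysis in the trial (SAP 8.6.6 plans none for safety). SAP 1 also requires the SAP to be final before enrollment and before programming starts. Any repair made afterwards would be a change to primary-analysis code in a finalized plan.

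**Working it through.** The plan gives no figure to reproduce, because the sample size was not based on power (SAP 5). The check is one of estimability: a linear function L of the fixed effects is estimable only if L is a combination of the rows of the fixed-effects matrix X, that is, if rank[X; L] = rank[X]. SAS was not run.

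**Inputs**

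- Design: reference on Day 1, test on Day 9, one sequence (SAP 4; Protocol 5.5).
- Terms: the MODEL and BY lines in SAP 8.5.3.
- Assumed: 12 completers, the number planned in SAP 5.
- Assumed: the contents of `aperiod` and `pkday`. Both readings of each are tried.

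Columns are intercept, treatment 1, treatment 2, `aperiod`, `trtseqp`. The contrast is L = (0, −1, 1, 0, 0).

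**1. `aperiod` = 1 on Day 1 and 2 on Day 9, both days in one fit.** SAP 8.5.1.4 supports this reading, since it speaks of treatment periods: "Any quantifiable predose concentration value in the first treatment period will be considered anomalous".

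- Only two row types occur: r1 = (1, 1, 0, 1, 1) and r2 = (1, 0, 1, 2, 1). The rank is 2 of 5 columns.
- To match the treatment columns of L we need −r1 + r2 = (0, −1, 1, 1, 0). The `aperiod` entry is 1 and not 0, so the contrast is not estimable.
- The LS means at mean `aperiod` (1 + 2)/2 = 1.5 are (1, 1, 0, 1.5, 1) and (1, 0, 1, 1.5, 1). The treatment columns force r1 and r2 respectively, whose `aperiod` entries are 1 and 2. Neither LS mean is estimable.
- Putting `aperiod` in CLASS gives rank 2 of 6 columns and the same result.

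**2. `aperiod` constant, both days in one fit.** The rows are (1, 1, 0, 1, 1) and (1, 0, 1, 1, 1). Their difference is exactly L, and each LS-mean vector is one of the rows. All three quantities are estimable.

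**3. `pkday` = study day.** SAP 3.1 defines the endpoints on Days 1 and 9, and SAP 8.5.3 refers to each dosing day. Each BY group then has one row type (rank 1) and one record per subject. There is no treatment difference, and between- and within-subject variance cannot be separated. This holds even with the text model.

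**4. Text model.** The rows are (1, 1, 0) and (1, 0, 1), rank 2 of 3. The difference is (0, −1, 1), so all three quantities are estimable. With 12 complete pairs this is a paired t analysis of the logs, with 12 − 1 = 11 df and t = 1.796 for the 90% CI.

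| Reading of the code | Rank | Ratio and 90% CI? |
|---|---|---|
| `aperiod` 1/2, `pkday` does not split days | 2 of 5 | No |
| `aperiod` constant, `pkday` does not split days | 2 of 5 | Yes |
| `aperiod` 1/2, `pkday` = study day | 1 | No |
| `aperiod` constant, `pkday` = study day | 1 | No |
| Text model, one fit | 2 of 3 | Yes |

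One of the four code readings works. That is a count of readings, not a probability.

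**5. Sample size.** Repeating the check with 14 completers, 1000 completers, or 12 completers plus 2 Day-1-only subjects gives the same answers, because only two row types ever occur.

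**6. `trtseqp`.** With one sequence it is constant. Removing `aperiod` but keeping a constant sequence column leaves the contrast estimable, so this term is redundant rather than harmful. It is not listed in CLASS, however. If it is a character variable the step would be expected to stop, a point the algebra does not test.

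**The case against.** The governing text is complete, correct and estimable. It names the model, test, reference, interval and back-transformation. The code is labelled as an example and has unfilled data-set names. The SAP carries other template remnants, such as a placebo example in section 6 and excretion parameters in 8.5.2. A programmer whose first run produced no ratio would go back to the paragraph above the code. No wrong estimate would be reported.

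The `pkday` point rests on an assumed meaning. SAP 8.5.3 speaks of fitting each parameter separately, and the code requests a comparison against control within each BY group, so its author evidently expected both treatments to be present. The CLASS point depends on a variable type the SAP does not give.

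Much of this stands. It limits the consequence to a visible failure with an obvious repair, and it makes `pkday` and CLASS matters to clarify rather than demonstrated faults. It does not remove the mismatch: the heading says the code will be used, no rule in the SAP ranks text above code, and the added model terms appear nowhere in the stated model under any reading.

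**Conclusion.** The concern holds. The mismatch between text and code is certain and depends on no assumption. The consequence does depend on the undefined variables. If `aperiod` is the treatment period, as SAP 8.5.1.4 suggests, 0 of 3 quantities (the difference and the two LS means) are estimable. If `pkday` is the study day, neither the ratio nor the within-subject CV exists. In either case the code gives no geometric mean ratio or 90% CI for any of the three primary parameters. If `aperiod` is constant, `pkday` does not split the days and `trtseqp` is numeric, the code works.

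The stated analysis is sound and need not change. This is a correction that should be made, not a threat to the trial's conclusion.

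**What to change.** Bring the example code into line with the text:

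1. Take `pkday` out of BY, or define it and confirm that it does not separate Days 1 and 9.
2. Use `model l_pk = trtan / cl residual ddfm = kr;`
3. Use `random intercept / subject = usubjid;`

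The other statements can stay. `alpha = 0.1` agrees with the 90% CI, and `control('1')` agrees with sotorasib alone being first in SAP Table 1, provided `trtan` follows that order.

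Add one sentence saying that period and treatment are confounded by design. The code does not need it to run, but it tells the reader why no period term can be fitted.

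The cost is three code lines and one sentence in the SAP, with no protocol amendment and no extra data or subjects.

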8.6. Safety and Tolerability Assessments

8.6.1. Adverse Events

All AEs will be coded using the Medical Dictionary for Regulatory Activities (MedDRA) Version 25.0. (or higher if a new version is issued during the study; see the DMP for more details).

A treatment-emergent adverse event (TEAE) will be defined as an AE that starts during or after the first dose, or starts prior to the first dose and increases in severity after the first dose.

A treatment related TEAE will be defined as a TEAE with a relationship of possibly related or related to the study treatment, as determined by the investigator.

All AEs will be listed. In addition to the data recorded in the database, the listings will include derived onset time and duration. Onset time will be calculated from the time of dosing for TEAEs only.

The frequency of subjects with TEAEs and the number of TEAEs will be summarized for the following categories:

- TEAEs (overall, serious, leading to discontinuation, and leading to death) by treatment
- TEAEs by severity and treatment
- Treatment-related TEAEs (overall, serious, leading to discontinuation, and leading to death) by treatment
- Treatment-related TEAEs by severity and treatment

The frequency of subjects will be summarized separately for TEAEs and treatment-related TEAEs by the following:

- System organ class, preferred term, severity and treatment
- Preferred term, severity and treatment

For the AE data the following rules will apply:

- For the derivation of TEAE status: If the start date/time of an AE is incomplete or missing, an AE will be assumed to be a TEAE, unless the incomplete start date/time or the end date/time indicates an AE started prior to the first dose.
- For the derivation of treatment-related TEAE status: If the study treatment relationship for a TEAE is missing, a TEAE will be assumed to be a treatment-related TEAE.
- For the derivation of onset time (applicable to TEAEs only): If the start date/time of a TEAE is missing, onset time will not be calculated. If the start date/time of a TEAE is incomplete, where possible, the minimum possible onset time will be calculated and presented in '≥DD:HH:MM' format (eg, if the date/time of the last associated dose is 01MAY2019/08:00 and recorded start date/time of a TEAE is 03MAY2019, then the minimum possible onset time will be calculated by assuming a TEAE started at the first hour and minute of 03MAY2019 [03MAY2019/00:00], thus will be presented as onset time ≥01:16:00 in the listing). If the start date of a TEAE is the same as the date of the last associated dose but the start time of a TEAE is missing, an onset time will be presented as '≥00:00:01'. Any clock changes will be accounted for in the derivation.
- For the derivation of duration (applicable to all AEs): If the end date/time of an AE is missing, duration will not be calculated. If the start or end date/time of an AE is

incomplete, where possible, the maximum possible duration will be calculated and presented in ‘ \leq DD:HH:MM’ format (eg, if the start of an AE date/time is 01MAY2019/08:00 and its recorded end date/time is 03MAY2019, then the maximum possible duration will be calculated by assuming an AE ended at the last hour and minute of 03MAY2019 [03MAY2019/23:59], thus will be presented as duration \leq 02:15:59 in the listing). Any clock changes will be accounted for in the derivation.

- For the calculation of TEAE summary statistics: If the severity of a TEAE is missing, that TEAE will be counted under the ‘missing’ category.
- For the calculation of TEAE summary statistics: If a subject experienced multiple TEAEs with the same preferred term for the same treatment, this will be counted as 1 TEAE for that treatment under the maximum severity recorded.

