8.4. Safety Analysis

The number and percentage of subjects reporting any adverse events will be tabulated by Medical Dictionary for Regulatory Activities system organ class and preferred term. Tables of fatal adverse events, serious adverse events, adverse events leading to withdrawal from investigational product or other protocol-required therapies, and significant treatment-emergent adverse events will also be provided. Subject-level data may be provided instead of tables if the subject incidence is low.

Endpoints for clinical laboratory tests, ECG, and vital signs will be summarized.

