5. SAMPLE SIZE JUSTIFICATION

Approximately 14 subjects will be enrolled in order that approximately 12 subjects complete the study. The sample size for this study was based upon precedent set by other PK studies of a similar nature and was not based on power calculations.

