6. STUDY TREATMENTS

The study treatment names, abbreviations, and ordering to be used in the TFLs are presented in [Table 1](#).

Table 1: Presentation of Study Treatments in TFLs

Study Treatment	Order in TFLs
Sotorasib administered alone	1
Omeprazole coadministered with Sotorasib and an acidic beverage	2

All TFLs will be based on actual treatments (eg, if subject was assigned to receive placebo but was wrongfully dosed with active treatment they would be summarized and listed under active treatment).

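### SAP 8.6.1 promises the number of TEAEs, but its rule for repeats of a preferred term, read literally, makes that number lower than the recorded events whenever a term recurs in a subject on one treatment

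*SAP*

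**What the plan says.** SAP 8.6.1 plans two kinds of TEAE table.

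- **Overview and by-severity summaries.** These carry both measures: "The frequency of subjects with TEAEs and the number of TEAEs will be summarized for the following categories". The categories are TEAEs overall, serious, leading to discontinuation and leading to death; TEAEs by severity; and the treatment-related versions of these. All are by treatment.
- **System organ class and preferred-term tables.** These carry subjects only: "The frequency of subjects will be summarized separately for TEAEs and treatment-related TEAEs by the following".

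Among the derivation rules at the end of the section is this one: "For the calculation of TEAE summary statistics: If a subject experienced multiple TEAEs with the same preferred term for the same treatment", then "this will be counted as 1 TEAE for that treatment under the maximum severity recorded".

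Individual events stay visible in the listing: "All AEs will be listed". Protocol 8.4 (Safety Analysis) asks only for subjects: "The number and percentage of subjects reporting any adverse events will be tabulated by Medical Dictionary for Regulatory Activities system organ class and preferred term". SAP 6 (Study Treatments) defines two treatment columns, sotorasib alone and "Omeprazole coadministered with Sotorasib and an acidic beverage".

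**The concern.** Counting a subject once per preferred term at the worst severity is the usual and correct rule for a subject frequency. It is not a rule for counting events. The sentence does not say that the subject is counted once; it says that several TEAEs are counted as one TEAE. Its scope is TEAE summary statistics generally, and nothing else in the section exempts the event count.

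The only tables planned to carry an event count are the overview and by-severity summaries. If repeats are collapsed there, no summary table gives the number of recorded TEAEs. Three things follow when a term recurs:

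- the table total falls below the number of TEAEs in the listing;
- the milder repeats vanish from the severity counts;
- two programmers could reasonably produce different numbers, one reading the rule literally and the other applying it to subject counts only.

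Recurrence is plausible. Protocol 1.4.1.2 (Risks) names diarrhea, nausea, vomiting and abdominal pain for both sotorasib and omeprazole.

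**Working it through.** The plan states no figure on this point that could be reproduced. The check is to apply the rule and compare the result with a plain count of records.

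**Inputs from the documents**

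- Measures promised: subjects and number of TEAEs (SAP 8.6.1, overview and by-severity summaries).
- Unit within which repeats collapse: same subject, same treatment, same preferred term (SAP 8.6.1).
- Treatment columns: two (SAP 6).
- Subjects: about 14 enrolled and about 12 completing (SAP 5).

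**Input not in the documents:** how often a term recurs in a subject on one treatment. This is assumed below.

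**Formula.** Let R be the number of recorded TEAEs and D the number of distinct subject-treatment-term combinations. The rule reports D where the label promises R. With m = R/D, the relative understatement is

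(R - D)/R = 1 - 1/m.

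Since D can never exceed R, the rule can only lower the count.

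**Worked example (assumed data).** Subject 1 has three headaches on sotorasib alone, of severity 1, 2 and 1. Subject 2 has one nausea of severity 1 on each treatment.

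| Quantity | Every record | SAP rule |
|---|---|---|
| TEAEs, sotorasib alone | 4 | 2 |
| TEAEs, combination | 1 | 1 |
| TEAEs, both columns | 5 | 3 |
| of which severity 1 | 4 | 2 |
| of which severity 2 | 1 | 1 |
| Subjects with any TEAE | 2 | 2 |

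Here m = 5/3 and the understatement is 1 - 3/5 = 40%. Both lost events are of severity 1. The number of subjects does not move.

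**Range over the assumed m**

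| m | 1 - 1/m |
|---|---|
| 1.0 (no repeats) | 0% |
| 1.1 | 9.1% |
| 1.25 | 20.0% |
| 1.5 | 33.3% |
| 2.0 | 50.0% |

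**Is the rule needed to merge duplicate records?** Protocol Appendix 1 already has an event whose severity changes between onset and resolution entered once, at its worst severity. Several records of one term in one subject should therefore generally be separate episodes, so collapsing them loses events rather than removing duplicates.

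**The case against.** The strongest reply is that the rule is pre-specified and reproducible. It says exactly which records are merged and at what severity, so the quantity is defined and the complaint is about its label. That stands in part: relabelling would be an adequate remedy. It does not remove the conflict, because a reader of a column headed as the number of TEAEs will take it to count events.

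A second reply is that the rule was meant only for subject frequencies. That is possible. SAP 1 (Introduction) places the detailed table layouts in a separate shells document that is not available here and may show this. The SAP text does not say so.

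A third is that little depends on it. This also stands. Safety is a secondary objective, SAP 8.6.6 plans no inferential safety analysis, and Protocol 8.4 promises only subject counts and allows subject-level data in place of tables when incidence is low. With about 14 subjects, every episode can be read from the listing.

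A reader might infer three stronger things that the documents do not support:

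- **That the reported counts are certain to be too low.** They are low only if a subject has the same term more than once on one treatment. With no repeats the two counts agree.
- **That a given term, such as diarrhea, would be understated by half in a table.** No planned table gives event counts by preferred term. In the overview and severity summaries, any lost events are spread over all terms.
- **That the collapsed count is merely the subject count again.** A subject with nausea, headache and diarrhea on one treatment is one subject but three TEAEs under the rule.

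**Conclusion.** The point holds as an internal inconsistency in SAP 8.6.1, of low severity. On a literal reading, the event counts in the overview and by-severity summaries are counts of distinct subject-by-term combinations within each treatment. They will be lower than the number of recorded TEAEs, and will disagree with the listing, whenever a term recurs within a subject and treatment.

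The direction is certain, but the size cannot be derived from the documents: it depends wholly on the assumed m. The conclusion also assumes that the shells do not restrict the rule to subject frequencies. Those frequencies, the preferred-term tables and the primary pharmacokinetic analysis are untouched, and no trial conclusion is shown to change.

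**What to change.** Amend the rule in SAP 8.6.1 so that it governs subject frequencies only: within a treatment, a subject counts once per preferred term, at the maximum severity. Add that the number of TEAEs counts every recorded TEAE, each at its own severity, and check that the shells agree.

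If collapsing is intended, keep the rule but relabel the quantity as the number of distinct subject-by-preferred-term TEAEs per treatment, so that nobody tries to reconcile it with the listing.

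Either change takes a sentence or two and needs no new data or procedures. The only consequence of the first option is that event counts will be somewhat higher than under the collapsing rule if terms recur.
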